PUBLISH DATE JUNE 20, 2018

STATISTICAL ANALYSIS PLAN

TITLE: A comparison of early deployment of a video capsule (Endocapsule EC-10: Olympus Tokyo. Japan) in the Emergency Department versus conventional work-up of non-hematemesis gastrointestinal bleeding [NHGIB].

NCT02442830

[name], PHD, PRINCIPAL INVESTIGATOR

STATISTICAL ANALYSIS PLAN

Study outcomes:

The primary outcome for this study was the rate of localization of bleeding during hospitalization. Localization of bleeding was defined as identification of blood or identification of a lesion with high-risk stigmata of recent hemorrhage (SRH). Secondary outcomes included, overall rate of localization of bleeding by the end of admission, anatomic location of bleeding or the bleeding source, rate of endoscopic therapy, rate of readmission, rate of diagnosis of vascular lesions (defined as Dieulafoy's lesions or angioectasias), rate of re-bleeding within 30 days of discharge, rate of all-cause mortality within 30 days of hospitalization, cumulative direct hospital costs by the end of admission, and overall rate of identifying the etiologic diagnosis.

Sample size calculation:

The study was planned as a superiority trial and the estimated probability of localization of bleeding during hospitalization in the Early Capsule arm to be two times greater than that of the Standard of Care arm (i.e. estimated hazard ratio of 2.00). We found no prior studies similar to our methodology, so prior experience at our institution guided the estimation of effect. Power analysis revealed that for this effect size to be detected (80% chance) as significant at the 5% level, a sample of at least 72 patients (36 per group) would be required.

Statistical analysis:

Patient characteristics were described as means with standard deviation (SD) or as proportions. Time to localization and time to first procedure were described using medians with interquartile range (IQR). Hospital costs were described in US dollars (USD).

Independent variables selected for analysis included those previously suggested as prognostic indices for NHGIB. Variables chosen for analysis included gender, race, age, vital signs at admission, use of anticoagulants, use of non-steroidal anti-inflammatory drugs (e.g. aspirin and ibuprofen; NSAIDs), use of a P2Y₁₂ inhibitor (e.g. clopidogrel), factors that contribute to the Glasgow-Blatchford Score, and type of bleeding at admission (i.e. hematochezia, melena, or symptomatic anemia).

Univariate analyses involved Wilcoxon-Rank sum tests for continuous variables and Chi-square or Fisher's Exact tests for binary variables. A Kaplan-Meier survival analysis with a Log-rank test compared the cumulative incidence of endoscopic localization of bleeding for the two groups. For multivariate analyses, independent variables with a difference at $p<0.10$ following univariate analysis or those noted to be unevenly distributed between the two cohorts were included as covariates. A p -value of less than 0.05 was significant. Statistical analysis was performed using STATA 13.

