The use of capsule endoscopy has been approved by the FDA since 2001 for small intestinal bleeding obscure GI Bleeding]. It is very safe, no deaths associated with its use have been reported. More than two million capsule have been used and obstruction and perforation are extremely rare.

Interest in the broader use of VCE is accumulation. In 2004 Sachdev et al reported a pilot study on the use of early use of VCE in acute NHGIB. This showed a 50% reduction to time to diagnosis in 24 patients. More recently studies of VCE deployed in the ED, in patients with upper GI bleeding showed improved management. Our group recently demonstrated that the closer a video capsule is performed to the time of bleeding the higher the likelihood of locating the sources and the higher the therapeutic intervention rate.³ We also have demonstrated that the use of capsule endoscopy in patients with NHGIB has a higher diagnostic yield than does colonoscopy. With improved diagnostic yields, capsule endoscopy may help clinicians by providing guidance in the management of patients with NHGIB.

This protocol is be the first attempt to prospectively examine this concept in a large randomized prospective trial. The questions are, can early capsule intervention decrease time to diagnosis, numbers of procedures and hospital length of stay in patients with non-hematemesis gastrointestinal bleeding.

References:

1. Jawaid S GB, Singh, A, Marshall C, and Cave D. . The epidemiology of gastrointestinal bleeding in an academic emergency department as a basis for

INVESTIGATOR STUDY PLAN - REQUIRED

reconfiguring the conventional approach to its diagnosis and management. .
Gastrointestinal Endoscopy 2013;77:Supplement, Page AB483.

5) Inclusion and Exclusion Criteria*

Inclusion Criteria:

- Age greater than 18 years old
- New onset of melena or hematochezia
- Able to sign consent
- Hemodynamically stable (i.e. blood pressure >100/60 or pulse <110 at the time of consent)

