- ED must plan to admit patient to the hospital or Clinical Decision Unit.

Exclusion criteria:

- Adults unable to consent
- Individuals who are not yet adults (infants, children, teenagers)
- Pregnant women
- Prisoners
- Prior history of gastroparesis
- Prior history of gastric, or small bowel surgery
- Prior history of inflammatory bowel disease
- Concern for infectious colitis
- Non-English speaking
- Evidence of dysphagia at the time of presentation
- Presence of bright red blood per rectum
- Allergy to metoclopramide or erythromycin
- Code status of DNR/DNI or CMO
- Prior history of abdominal radiation
- Presence of ICD or pacemaker or other implanted electronic devices
- Abdominal pain suggesting an acute abdomen or obstruction. In clinical practice, only patients with crampy abdominal pain due to

INVESTIGATOR STUDY PLAN - REQUIRED

Crohn's disease, previous intestinal surgery and a previous history of radiation therapy require a patency capsule or CT enterography before capsule endoscopy.

- Patients who cannot undergo surgery

6) Study-Wide Number of Subjects*

Not applicable – not a multi-site study

7) Study-Wide Recruitment Methods*

Not applicable – not a multi-site study

8) Study Timelines*

1. The participation of individual subjects in this study will be approximately 31-40 days (the length of their hospitalization plus an additional thirty days for follow up).
2. The duration anticipated to enroll all study subjects is about 24 months.
3. The estimated date for the investigators to complete this study and data analysis is two years.

9) Study Endpoints*

The primary endpoint will be time to diagnosis. Secondary endpoints will include hospital length of stay, number of invasive procedures, blood product transfusions.

10) Procedures Involved*

Screening

Patients presenting to the Emergency Room with NHGIB (defined as melena or hematochezia) will be identified by a member of the ED staff.

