During hospitalization, data will be recorded from ED pulse check, Meditech, Soarian, and Allscripts regarding fluid administration, transfusion of pRBC, initial hematocrit, times and types of procedures (e.g. upper endoscopy, enteroscopy, colonoscopy), time from entry to ED to time to diagnosis (i.e. localization of source of bleeding), admission disposition (i.e. clinical decision unit, regular floor, ICU), time of discharge. The procedures involved in the hospitalization (i.e. upper endoscopy, enteroscopy, and colonoscopy) will be done as part of standard of care. All of this information will be linked to the subject’s study ID number as described above. This data collection is for research purposes only.

In addition, the costs of the procedures will be collected through financial services. The costs that will be collected are both the fixed and variable costs associated with each patient in the study. We will also collect the direct and indirect costs allocated to each patient. All charges associated with the admission for each patient in the study will have costs allocated. This will be evaluated as an additional data point to compare the two arms of the study. No additional PHI will be collected.

Telephone Follow-Up

Subjects will also be contacted by phone by a research staff member at two different time points following their discharge from the hospital. These time points will be at 3 days (+2 days) and 30 days (+/- 3 days) following their discharge. At these time points a staff member will call a subject to obtain information about whether or not a patient has had recurrent bleeding and whether or not the patient had to be readmitted to a hospital or emergency room for

INVESTIGATOR STUDY PLAN - REQUIRED

recurrent bleeding. Please see attached form for telephone script that staff member will read along with particular questions that will be asked.

No more than three attempts will be made at each time point to reach the subject. If a message is left, it will be "Hello, this is [name] calling from UMass looking to speak with [subject]. Please call back at [number] at your earliest convenience. Thank you."

11) Data and Specimen Banking*

N/A – no data banking.

12) Data Management*

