- Data analysis plan: As discussed above, data will be obtained through review of medical records. Specifically we will be looking at time to diagnosis of bleeding source, laboratory values, number of blood products transfused procedures performed, along with additional measures as described above. Once we have separated our two cohorts we will perform chi-square and standard t-tests to compare the different dependent variables in the two cohorts. We will also perform Kaplan-Meier curve analyses to compare length of stays and time to diagnosis which is the primary metric of this study.
- Steps that will be taken to secure data: All clinical data from individual subjects will be de-identified and given a study number. The study number will serve as a link between the data and the subject's identifiable information. RedCAP online encrypted database will be used to store the dataset. The database will only be accessed by the primary investigator and research assistants.
- Data will be exported for analysis as a de-identified data set. The de-identified dataset (which would be absent of any PHI) would be transferred in a password-encrypted email to the external sponsor.
- The external sponsor – Olympus Medical Systems – will have access only to the de-identified data set and will not have access to the study key with identifying health information.
- Identifier keys will be destroyed once primary data analysis is complete.
- No identifying information will be used in any report or publication generated from this study.
- Power analysis: Based on a previous retrospective epidemiology study, the average time to diagnosis for subjects presenting with non-hematemesis GI bleeding (NHGIB) who underwent a conventional workup was 30 hours (standard deviation of 6.1). Subjects with NHGIB who had an early capsule as the first diagnostic test had an average time to diagnosis of 15.9 hours (standard deviation of 12.2). This calculates an effect size of 1.49301. This is

INVESTIGATOR STUDY PLAN - REQUIRED

an effect we are looking to replicate prospectively in this study. Using this data with an assumed α of 0.05 and using a sample size of 80 subjects in the early capsule deployment group and 80 subjects in the Conventional Workup group the calculated power is 99%.

13) Provisions to Monitor the Data to Ensure the Safety of Subjects*

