latter figure is for a study on Crohn's disease patients. If capsule retention occurs subjects may require radiologic imaging. This usually consists of a plain film of the abdomen taken 2 weeks after the capsule was swallowed to localize the capsule. They will not be kept in hospital for this. If the patient sees the capsule in their feces, this test is not needed.

Importantly, even if the capsule is retained subsequent clinical decompensation requiring endoscopic or surgical intervention is extremely rare. In most cases of capsule retention, clinical decompensation does not occur and no further therapeutic options need to be pursued. In fact, if a capsule is retained it can often be useful in defining the site of luminal abnormality that can be targeted by a clinician. Nonetheless, to minimize the risk of capsule retention in our subjects we will be screening all potential subjects for associated conditions that are commonly associated with this complication. These conditions are listed as part of our exclusion criteria for this study. Removal of a capsule may be achieved by deep enteroscopy or at the time of surgery which is usually performed to remove the cause of the retention e.g. a tumor or stricture. The capsules may be left in place, Patients have been known to safely retain the capsule for years without ill effects.

It is not expected that there is any risk that the subjects assigned to the early capsule group will require more diagnostic procedures than the conventional work-up group. The hypothesis of this study is that the early deployment group may, in fact, undergo fewer procedures and have a shorter hospitalization compared to those having a conventional work-up.

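### The SAP omits the protocol's three secondary endpoints without a stated reason, and leaves its reworded primary and its power statement under-specified

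*SAP*

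**What the plan says.** **Protocol.** Section 9 (Study Endpoints) reads: "The primary endpoint will be time to diagnosis. Secondary endpoints will include hospital length of stay, number of invasive procedures, blood product transfusions". Section 10 (Review and Follow-Up) records "time from entry to ED to time to diagnosis (i.e. localization of source of bleeding", so diagnosis means localization and the clock starts at ED entry. Section 12 (Data Management) plans "Kaplan-Meier curve analyses to compare length of stays and time to diagnosis which is the primary metric of this study", with chi-square and t-tests for the other variables, which include transfusions and procedures.

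Two of the three secondaries are central to the trial's purpose. Section 4 (Background) asks "can early capsule intervention decrease time to diagnosis, numbers of procedures and hospital length of stay", and section 15 (Risks to Subjects) states: "The hypothesis of this study is that the early deployment group may, in fact, undergo fewer procedures and have a shorter hospitalization".

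**SAP.** Study outcomes reads: "The primary outcome for this study was the rate of localization of bleeding during hospitalization". Localization there means seeing blood or a lesion with high-risk stigmata. Nine secondaries follow, among them the overall localization rate by the end of admission. Length of stay, procedure count and transfusions are not among them. The Sample size section describes a localization probability twice as high with the capsule, equates this with a hazard ratio of 2.00, and asks for at least 72 patients (36 per group) for 80% power at the 5% level. The Statistical analysis section compares endoscopic localization by Kaplan-Meier and log-rank, and reports time to localization as a median with IQR.

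**The concern.** There are three linked gaps.

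- **Missing secondaries.** Someone working from the SAP alone would report nothing comparative on procedures or length of stay, which the trial set out to test, nor on transfusions. The SAP neither mentions the protocol's list nor explains the difference.
- **Under-defined primary.** The word rate can mean a proportion or an event rate over time. The SAP gives no time origin and does not say how patients discharged without localization enter the Kaplan-Meier analysis. Its log-rank sentence covers endoscopic localization, a qualifier that its outcome definition lacks. A strategy that is faster but no more complete would succeed on a time to event and fail on a proportion, so the type must be stated.
- **Sizing.** A doubled probability and a hazard ratio of 2.00 are different effects. The power of 72 patients also depends on how many are localized, which the SAP does not state.

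**Working it through.** **1. Outcomes side by side**

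| Protocol section 9 | In the SAP |
|---|---|
| Time to diagnosis (primary) | Localization rate during hospitalization (primary); time to localization as median and IQR |
| Length of stay | Not listed |
| Number of invasive procedures | Not listed; time to first procedure is described, but it is not a count |
| Transfusions | Not listed |

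Some items on the SAP's secondary list were already planned. For costs, protocol section 10 says "This will be evaluated as an additional data point to compare the two arms of the study". Its telephone follow-up asks "whether or not a patient has had recurrent bleeding and whether or not the patient had to be readmitted".

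**2. Reproducing the SAP's 72**

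Inputs from the SAP: hazard ratio 2.00, 5% level, 80% power, equal arms. The SAP does not state sidedness; two-sided is assumed, so (1.960 + 0.842)² ≈ 7.849.

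- Freedman: ((1 + 2)/(2 − 1))² × 7.849 = 9 × 7.849 = 70.6, so 71 events. As 36 per arm this is 72.
- Schoenfeld: 4 × 7.849/(ln 2)² = 65.3, so 66 events.
- One-sided versions give 56 and 52, and neither matches.

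The stated size therefore reproduces as a time-to-event calculation in which nearly every patient has an event. A two-proportion calculation for a doubled probability comes near 35 per arm only if control is about 33% and capsule 66%, and the SAP gives no control rate. Time to event is the likelier basis.

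**3. Share of patients who must be localized**

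Schoenfeld: 65.3/72 = 91%. Freedman: 71/72 = 99%.

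**4. Doubled probability against a hazard ratio of 2.00**

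Under proportional hazards, doubling a control probability p implies HR = ln(1 − 2p)/ln(1 − p).

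- p = 20%: ln 0.60/ln 0.80 = 2.29
- p = 30%: ln 0.40/ln 0.70 = 2.57
- p = 40%: ln 0.20/ln 0.60 = 3.15

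None equals 2.00.

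**5. Power of 72 patients at a hazard ratio of 2.00**

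The documents give no control localization rate for this trial, so a range is assumed. Capsule localization is 1 − (1 − p)²; events are 36 × (control + capsule); power is Φ(√events × ln 2/2 − 1.960).

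| Control (assumed) | Capsule | Ratio | Events | Power | Total N for 66 events |
|---|---|---|---|---|---|
| 50% | 75% | 1.5 | 45.0 | 64% | 106 |
| 60% | 84% | 1.4 | 51.8 | 70% | 92 |
| 70% | 91% | 1.3 | 58.0 | 75% | 82 |
| 80% | 96% | 1.2 | 63.4 | 79% | 76 |

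The last column is 66 divided by the mean proportion localized, rounded up to an even number; at 50% it is 66/0.625 = 105.6. Simulated log-rank power at 36 per arm agrees: 64, 70, 75 or 76, and 78%.

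**The case against.** The strongest reply is that the primary has not really changed. The protocol equates diagnosis with localization and plans Kaplan-Meier; the SAP sizes on a hazard ratio and uses Kaplan-Meier with a log-rank test. A separate end-of-admission rate would be redundant if the primary were itself a proportion. This largely stands. A reader might infer that the trial switched from a time to event to a proportion. The documents do not support that: they show an incomplete definition, not a demonstrated switch.

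Second, protocol section 12 still plans methods for length of stay, procedures and transfusions. The SAP does not revoke it, and its wording does not say that its list is exhaustive. This softens the omission but does not cure it, since the SAP should carry the prespecified outcomes.

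Third, the protocol is dated April 2016 and the SAP June 2018, so an amendment not supplied here may give the reason. That is possible. A reader might also infer that outcomes were chosen after the data were seen. Nothing in the documents shows this; they show only that no reason or date is given.

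Fourth, the SAP calls 72 a minimum and the protocol plans up to 160. With 160 patients the same formula gives 93–98% power over the same assumed range. This limits the practical consequence but does not correct the stated basis for 72.

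Finally, protocol section 10 has capsule patients with no finding considered for early discharge. A reader might infer that the log-rank test is biased toward the capsule. The documents give neither a censoring rule nor discharge times, and any figure would depend on the times assumed. The point is a precaution against silence, not a shown bias.

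**Conclusion.** The point holds. The omission of length of stay, procedure count and transfusions from the SAP is established by the text, needs no assumption, and is unexplained in these documents. It is the most serious part, because two of the three are questions the protocol set out to answer.

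The primary is most likely the protocol's own time to event in different words. Its time origin, its event and the handling of discharge without localization still need to be stated.

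The equation of a doubled probability with a hazard ratio of 2.00 is wrong under proportional hazards. At that hazard ratio, 72 patients give 80% power only if about 91–99% are localized. The 64–79% range rests on proportional hazards, a two-sided 5% test and an assumed control localization of 50–80%.

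**What to change.** 1. Restore length of stay, number of invasive procedures and transfusions as SAP secondaries, with methods consistent with protocol section 12 (for example, Kaplan-Meier for length of stay).
2. State the primary as time from ED entry to localization, compared by the log-rank test, with one event definition that reconciles the Study outcomes and Statistical analysis sections. Keep the end-of-admission rate as the binary secondary.
3. Do not treat discharge without localization as non-informative censoring. Keep such patients at risk to a stated common horizon, or use an equivalent method.
4. Delete the doubled probability, keep the hazard ratio, and restate the power with the required events and the assumed proportion localized.
5. For each outcome that differs from protocol section 9, give the reason and the date relative to data access, noting that costs, readmission and recurrent bleeding were already planned data items.

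The cost is SAP wording, a few routine analyses, and a stated power that may become less favourable. Protocol section 10 already records time from ED entry to diagnosis, procedure times and types, red-cell transfusion and discharge time, so no new data are needed.

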Depending on the findings a recommendation will be made as to the next most appropriate test. See attached Figure 1. If blood is found in the esophagus, stomach or duodenum an upper endoscopy is recommended. If blood is seen in the small intestine, it will be recommended that the subject next have a push enteroscopy, deep enteroscopy, or angiography. If blood in right colon, colonoscopy may be performed or deferred to colonoscopy as an outpatient, if active bleeding has ceased. If the capsule study is not diagnostic and no blood is seen in the GI tract and there is no ongoing hematochezia, the subject will be placed in ED observation for up to 23 hours and evaluated for potential discharge and follow-up by gastroenterology as an outpatient.

INVESTIGATOR STUDY PLAN - REQUIRED

If no bleeding/ blood or a likely source is found. These individuals will be considered for observation, early discharge and follow up in the GI outpatient setting.

For most subjects, the capsule will pass in a bowel movement within 24 - 72 hours of ingestion.

An equal number subjects [up to 80] will be randomized to the “conventional workup group”. “Conventional Workup” for NHGIB could include upper endoscopy, colonoscopy, and additional capsule or small bowel enteroscopy depending on the subject’s presentation and the results of the workup performed by the gastroenterology team. For some subjects, the VCE would be done as part of standard of care estimated that 5-15% of patients will have small intestinal bleeding. For patients requiring a video capsule endoscopy as part of “conventional workup” the patients will be given the same Olympus video capsule that is used in the “Early Capsule” group. Further management would be as standard of care. These subjects will be discharged on the recommendation of the attending hospitalist after completion of treatment.

Review and Follow-Up

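### Re-bleeding is counted from discharge, which the early-capsule strategy aims to bring forward, so the two arms' 30-day windows can start at different distances from the index bleed and in-hospital re-bleeds are never counted

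*SAP*

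**What the plan says.** SAP, Study outcomes, lists among the secondary outcomes the "rate of re-bleeding within 30 days of discharge". The same sentence includes readmission, with no window, and the "rate of all-cause mortality within 30 days of hospitalization".

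Protocol section 10, Telephone Follow-Up, gives the only stated way of learning about re-bleeding: calls after discharge. "These time points will be at 3 days (+2 days) and 30 days (+/- 3 days) following their discharge". The caller asks "whether or not a patient has had recurrent bleeding and whether or not the patient had to be readmitted". For the hospital stay, section 10, Review and Follow-Up, lists data "regarding fluid administration, transfusion of pRBC, initial hematocrit, times and types of procedures", followed by time to diagnosis, disposition and time of discharge. Re-bleeding is not on that list.

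The route to discharge differs by arm (section 10, Procedure). For early-capsule patients with no bleeding or likely source found: "These individuals will be considered for observation, early discharge and follow up in the GI outpatient setting". For the conventional arm: "These subjects will be discharged on the recommendation of the attending hospitalist after completion of treatment". Section 15 puts forward a shorter hospitalization with early capsule as a hypothesis, and section 9 makes length of stay a secondary endpoint.

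**The concern.** The time origin for re-bleeding is an event that follows randomisation and that the experimental strategy is meant to change. Suppose bleeding is most likely to recur in the first days and the conventional arm stays longer. More of that arm's high-risk time then passes in hospital, where re-bleeds do not count, while more of the early-capsule arm's falls inside the counted window. Two arms with the same re-bleeding process would show different rates, and the outcome would partly measure length of stay. Even with equal stays, a patient who re-bleeds on the ward and not after discharge is recorded as not having re-bled.

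At stake is how a secondary outcome is read. A reader would take a higher post-discharge rate after earlier discharge as harm, when it could come from the definition alone.

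**Working it through.** **The plan's own figure.** The documents give no expected rate or power for re-bleeding. Their one related figure is the SAP sample size of 72 (hazard ratio 2.00, 80% power, 5% level; two-sided assumed). Freedman's formula gives (1.960 + 0.842)² × [(1 + 2)/(2 − 1)]² = 7.849 × 9 = 70.6, so 71 events, or 72 when made even. It concerns localization of bleeding, and re-anchoring the re-bleeding window does not alter it.

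**Inputs from the documents.** The window is 30 days from discharge (SAP, Study outcomes). The only between-arm time gap given is in time to diagnosis, 30 − 15.9 = 14.1 hours, or 0.59 day (Protocol sections 12 and 25). It is used below as a stand-in for a gap in stay. Section 8 expects 31 to 40 days of participation, which implies stays of about 1 to 10 days.

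**Assumptions, not in the documents.** True 30-day risk of a first re-bleed is 15% in both arms, counted from randomisation. The hazard halves every h = 3, 5 or 10 days, or is constant. Stays are 2 days (early capsule) versus 4 days, or 2 versus 2.59 days.

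**Formula.** F(t) = 1 − exp{−A(1 − 2^(−t/h))}, with A set so that F(30) = 0.15. For a stay of L days, the rate counted under the SAP is F(L + 30) − F(L). The share lost before discharge is F(L).

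**Example, h = 3.** A = 0.1625/(1 − 2^(−10)) = 0.1627.
- Stay 2 days: F(32) − F(2) = 15.00% − 5.84% = 9.2%.
- Stay 4 days: F(34) − F(4) = 15.01% − 9.35% = 5.7%.
- Ratio from unrounded values: 1.62. True ratio: 1.00.

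| Hazard | 2 vs 4 days: counted rates | Ratio | Lost in hospital | 2 vs 2.59 days: ratio |
|---|---|---|---|---|
| Half-life 3 days | 9.2% vs 5.7% | 1.62 | 5.8% vs 9.3% | 1.15 |
| Half-life 5 days | 11.1% vs 8.3% | 1.34 | 3.9% vs 6.8% | 1.09 |
| Half-life 10 days | 12.9% vs 11.1% | 1.16 | 2.4% vs 4.4% | 1.05 |
| Constant | 14.8% vs 14.7% | 1.01 | 1.1% vs 2.1% | 1.00 |

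With equal stays the ratio is exactly 1. Taking in-hospital re-bleeders out of the denominator gives 1.56, 1.30, 1.14 and 1.00 for 2 versus 4 days, so the choice of denominator does not explain the effect. Counted over 30 days from randomisation, both arms show 15% in every row.

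**Effect on a test.** At the SAP's 36 per arm, the largest case is 36 × 9.2% = 3.3 expected patients versus 36 × 5.7% = 2.0, a difference of about one patient. Fisher's exact test would give p < 0.05 about 2% of the time at 36 per arm, and about 8% at the Protocol's 80 per arm.

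**Call window.** A final call at day 27 after discharge leaves days 28 to 30 of the SAP window unobserved. For a window from randomisation, the same call reaches day 30 for any stay of at least 3 days. A call at day 30 or later after discharge always does.

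**The case against.** The strongest reply is that post-discharge re-bleeding is a sensible outcome in itself. It describes what happens once patients go home, and it matches the planned calls. That stands, and it is a reason to keep the rate as descriptive. It does not make discharge a fair starting point for comparing randomised arms.

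The size is also open to dispute. Early discharge is considered only for capsule patients with no source found; those with findings go on to further procedures. A shorter stay overall is a hypothesis. A uniform two-day gap is therefore a generous assumption, and 1.62 is the extreme of the range shown. With the 14.1-hour stand-in the distortion is small, and under a constant hazard it all but vanishes. This stands as well.

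Some stronger readings are tempting but not supported:
- A reader might infer that re-bleeding is the main check that earlier discharge is safe. Protocol section 9 does not list it as an endpoint, and the SAP gives it no status above the other secondary outcomes.
- A reader might infer that the arms are followed for different lengths of time. Both windows last 30 days; only their position differs.
- A reader might treat the different wording for mortality as a further error. It most naturally means from admission, which is close to the anchor recommended here.
- A reader might fear a false claim of benefit. If stays shorten as hypothesised, the artefact runs against the early-capsule arm.

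**Conclusion.** The point holds as a limited one about a secondary outcome. The SAP starts the re-bleeding clock at an event after randomisation that the strategy is designed to move, and no outcome captures re-bleeding before discharge. Any distortion of the between-arm comparison needs two conditions that the documents do not establish: a re-bleeding hazard that falls with time, and a real difference in stay. If both hold, the illustrative spurious ratio is 1.05 to 1.62 across the gaps examined. If either fails, it is about 1.0. The loss of in-hospital re-bleeds needs neither condition. At the planned sizes the artefact would seldom reach significance alone, so the risk lies mainly in how the estimate is read.

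**What to change.** - Make the between-arm comparison of re-bleeding over a fixed 30 days from randomisation, with in-hospital re-bleeds included. Keep the rate within 30 days of discharge as descriptive.
- Give readmission a window too. Where the same 30 days from randomisation is used, report it with length of stay, because readmission can only follow discharge.
- Take in-hospital re-bleeds from the record systems already used for data collection. Write down, before abstraction, a definition that separates re-bleeding from continued index bleeding, and apply it the same way in both arms.
- If calls are still being made, schedule the last one no earlier than day 30 after discharge. The SAP is written in the past tense, so calls may be finished. In that case, supplement calls made before day 30 from the hospital record; for the window from randomisation, this matters only for stays under 3 days.
- Finish the abstraction before the identifier keys are destroyed, which Protocol section 12 plans once primary analysis is complete.

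The cost is a change of SAP wording and some chart abstraction. Classifying in-hospital re-bleeds will need some judgement, made in an open trial. Neither the primary outcome nor the sample size changes.
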